Description of change: Updated to correct the study drug names.
Rationale for change: Correction of an administrative/editorial error in the table.
2. **Section 6.5.3, Procedures for Participants Exhibiting Immune-Related Adverse Events (Table 11: Guidelines for Management of Immune-Related Adverse Events)**
Description of change: Revised the guidelines for ALT/AST and nephritis events.
Rationale for change: To apply permanent treatment discontinuation criteria to Grade 3 events.
3. **Section 6.7, Treatment After the End of the Study**
Description of change: Added a statement to clarify that participants will be supplied with study medication for up to 2 years if the study is terminated early.
Rationale for change: To clarify the availability of study medication to participants if the study is terminated early.
4. **Section 8.5.2, Whole Blood Correlative Flow Cytometry Assessments**
Description of change: Updated to clarify the timing of receptor occupancy analysis.
Rationale for change: To specify that an analysis of receptor occupancy, if performed, will occur following completion of the final study analysis.
5. **Incorporation of administrative changes.** Other minor, administrative changes have been incorporated throughout the Protocol and are noted in the redline version of the amendment.

Version 1-BE (06 JUL 2022)

Overall Rationale for the Amendment:

The primary purpose for this amendment is to address comments from the Belgium Health Authority.

1. **Section 1, Protocol Summary (Table 3: Schedule of Activities); Section 6.1, Study Treatments Administered; Section 8.3.3, Vital Signs**

Description of change: Added pre- and post-infusion vital sign monitoring for potential IRRs.

Rationale for change: To ensure that study participants are properly monitored for potential IRRs during and after administration of study drugs.

2. **Section 1, Protocol Summary (Table 3: Schedule of Activities); Section 8.3.4, Electrocardiograms**

Description of change: Added additional serial electrocardiograms to include Day 1 of each cycle through Cycle 5.

Rationale for change: Additional cardiac safety monitoring is justified based on emerging data from other LAG-3 targeting agents.

CTCAE	Common Terminology Criteria for Adverse Events
DCR	disease control rate
DOR	duration of response
DSMB	Data Safety Monitoring Board
ECG	electrocardiogram
ECOG	Eastern Cooperative Oncology Group
eCRF	electronic case report form
FDA	Food and Drug Administration
H1	hypothesis 1
H2	hypothesis 2
HPV	human papillomavirus
HR	hazard ration
irAE	immune-related adverse event
IRR	infusion-related reaction
IRT	interactive response technology
ITT	intent-to-treat
LAG-3	lymphocyte activation gene-3
MedDRA	Medical Dictionary for Regulatory Activities
NA	not assessed
NCI	National Cancer Institute
NE	not evaluable
ORR	objective response rate

Abbreviation	Definition
OS	overall survival
PD	progressive disease
PD-L1	programmed death-ligand 1
PFS	progression-free survival
PK	pharmacokinetic
PR	partial response
PT	preferred term
Q2W	once every 2 weeks
Q4W	once every 4 weeks
Q8W	once every 8 weeks
Q12W	once every 12 weeks
RECIST	Response Evaluation Criteria in Solid Tumors
R/M SCCHN	recurrent/metastatic squamous cell carcinoma of the head and neck
SAP	Statistical Analysis Plan
SD	stable disease
SOC	system organ class
T3	triiodothyronine
TEAE	treatment-emergent adverse event
TG	Treatment Group
TIM-3	t cell immunoglobulin and mucin domain 3
t _{max}	time to maximum concentration
ULN	upper limit of normal
WHO	World Health Organization

1. INTRODUCTION

This is a randomized, double-blind, controlled Phase 2 study to evaluate the efficacy and safety of the combination of retifanlimab plus INCAGN02385 (TG2) and retifanlimab plus INCAGN02385 and INCAGN02390 (TG3) compared with retifanlimab alone (TG1) as first-line treatment in participants with PD-L1–positive and systemic therapy–naïve R/M SCCHN.

Section 2 of the Protocol provides a detailed description of the investigational product, target patient population, rationale for doses to be examined, and potential risks and benefits of treatment with INCAGN02385, INCAGN02390, and retifanlimab.

After 30 participants have been randomized and have received treatment for at least 4 weeks (at least 2 doses), an interim analysis of safety will be performed by an independent external DSMB. Additional DSMB review of unblinded safety data will occur per the DSMB Charter.

The purpose of this SAP is to provide details of the statistical analyses that have been outlined in the INCAGN 2385-203 Protocol.

Population PK results will be provided by the Incyte pharmacokineticist and will appear in a separate report.

The analysis of biomarkers and pharmacodynamics will be conducted by the Incyte translational scientist, and the details of the analysis methodology and results will appear in a separate report.

2. STUDY INFORMATION, OBJECTIVES, AND ENDPOINTS

2.1. Protocol and Case Report Form Version

This SAP is based on INCAGN 2385-203 Protocol Amendment 2 dated 19 DEC 2023 and CRF approved 05 SEP 2024. Unless superseded by an amendment, this SAP will be effective for all subsequent Protocol amendments and eCRF versions.

2.2. Study Objectives and Endpoints

[Table 1](#) presents the primary and secondary objectives and endpoints.

Table 1: Objectives and Endpoints

Objectives	Endpoints
Primary	
To determine the efficacy of the combinations of retifanlimab + INCAGN02385 (TG2) and retifanlimab + INCAGN02385 + INCAGN02390 (TG3) compared with retifanlimab alone (TG1) in the overall study population.	Progression-free survival, defined as the interval between the date of randomization and the earliest date of disease progression, based on investigator assessment per RECIST v1.1, or death due to any cause.
Secondary	
To assess disease response using RECIST v1.1 in TG2 and TG3 compared with TG1.	
 Objective response, defined as having a CR or PR, determined based on investigator assessment per RECIST v1.1. DOR, defined as the time from earliest date of disease response (CR or PR) until earliest date of disease progression, based on investigator assessment per RECIST v1.1, or death from any cause if occurring sooner than progression. Disease control, defined as having CR, PR, or SD (≥ 6 months) as best response, based on investigator assessment per RECIST v1.1.
To determine the OS of TG2 and TG3 compared with TG1.	Overall survival, defined as the interval between the date of randomization until death due to any cause.
To determine the safety of TG2 and TG3 compared with TG1.	
 AEs, assessed in body systems with symptoms, through physical examinations, changes in vital signs and ECGs, and through clinical laboratory blood sample evaluations. Impact on study treatment, assessed by treatment interruptions, dose delays, and withdrawal of study treatment due to AEs.
Exploratory	

Table 1: Objectives and Endpoints (Continued)

Objectives	Endpoints
Exploratory (continued)	

3. STUDY DESIGN

This is a randomized, double-blind, controlled Phase 2 study to evaluate the efficacy and safety of the combination of retifanlimab plus INCAGN02385 and retifanlimab plus INCAGN02385 and INCAGN02390 compared with retifanlimab alone as first-line treatment in participants with PD-L1–positive, systemic therapy–naïve R/M SCCHN.

Approximately 162 participants will be randomized in a 1:1:1 ratio (approximately 54 participants per group) to 1 of the following treatment groups:

[figure not shown]
- TG1: retifanlimab plus placebo (INCAGN02385) and placebo (INCAGN02390)
- TG2: retifanlimab plus INCAGN02385 and placebo (INCAGN02390)
- TG3: retifanlimab plus INCAGN02385 and INCAGN02390

At randomization, participants will be stratified based on the following factors:

- LAG-3 expression status (determined centrally): positive ($\geq 5\%$) versus negative ($< 5\%$)
- PD-L1 CPS (determined centrally): 1%-19% versus $\geq 20\%$
- HPV p16 status (oropharyngeal only): p16-positive versus p16-negative;
HPV p16 status for participants without oropharynx cancer (eg, cancers of the oral cavity, hypopharynx, larynx) is considered HPV p16-negative.

The study design schema is shown in [Figure 1](#).

Figure 1: Study Design Schema

The study will include a 28-day screening period to determine eligibility, a treatment period in 4-week cycles for up to 2 years or until discontinuation criteria are met, an end-of-treatment visit, and 30-day and 90-day safety follow-up visits. Tumor assessments will be performed at baseline and subsequently Q8W for the first year of treatment and Q12W thereafter by site investigator review according to RECIST v1.1. Safety will be evaluated from the time the participant signs the informed consent form until the 90-day safety follow-up regardless of the start of a new anticancer therapy. Study treatment will begin on Day 1.

After 30 participants have been randomized and have received treatment for at least 4 weeks (at least 2 doses), an interim analysis of safety will be performed by an independent, external DSMB. Additional DSMB review of unblinded safety data will occur per the DSMB charter.

Details of the study design are in Section 4 of the Protocol.

3.1. Randomization

Approximately 162 participants will be randomized in a 1:1:1 ratio into 1 of 3 study treatment groups (ie, TG1, TG2, and TG3 with approximately 54 participants per group). Enrollment of participants whose tumors have low LAG-3 expression (ie, < 5%) will be capped at approximately 40% of the total.

3.2. Sample Size Considerations and Timing of Final Analysis

The sample size calculation is based on the primary endpoint of PFS. Approximately 162 participants will be randomized in a 1:1:1 ratio into TG1:TG2:TG3.

The final analysis will be performed after approximately 94 PFS events have been observed between TG1 and TG2 or between TG1 and TG3 (approximately 140 PFS events across the 3 treatment groups) or the last participant has been followed up for at least 8 months after randomization, whichever is earlier.

The sample size and power calculations were performed in R package "gsDesign" and as tabulated in [Table 2](#).

Table 2: Boundary Properties for Final Analysis of Progression-Free Survival Based on Potential Alpha Levels

Analysis	Value	$\alpha = 0.05$ (1-Sided)	$\alpha = 0.10$ (1-Sided)
Final	Z	1.645	1.2816
N: 108	p (1-sided)	0.0500	0.1000
Events: 94 (approximately 140 events across 3 treatment groups)	~HR at bound	0.7120	0.7670
Month: 20	P (Cross) if HR = 1	0.0500	0.1000
	P (Cross) if HR = 0.6	0.8000	0.8840

Based on a target of 94 PFS events for all participants at the final analysis between TG1 and TG2, which is expected to occur about 20 months from the start of enrollment if 108 participants are enrolled within 12 months, the study has approximately 80% power to detect an HR of 0.6 at an alpha level of 5% (1-sided), favoring a combination therapy versus TG1 with the assumption of study parameters as specified in Table 17 of the Protocol. When the 1-sided alpha level is 10%, the statistical power is 88.4%. The same assumption and sample size calculation approach is followed for TG3 and TG1.

The total sample size across the 3 treatment groups is calculated using 1.5 times the sample size from 2 treatment groups.

In case of delay in achieving the targeted number of PFS events, the primary analysis may be conducted when the last participant has been followed up for at least 8 months after randomization, even if the targeted number of events is not reached. In this case, the median PFS follow-up time across the blinded treatment groups will be quantified using the reverse Kaplan-Meier method and monitored by the study team. The study team will evaluate if the lower limit of the 95% CI for the median PFS follow-up time is achieved after 8 months.

[Table 3](#) shows the boundary properties for scenarios when the number of PFS events is approximately 108, 123, and 130 across the 3 treatment groups.

Table 3: Boundary Properties for Final Analysis of Progression-Free Survival Based on Different Number of PFS Events Across 2 Treatment Groups

Analysis	Value	$\alpha = 0.05$ (1-sided)	$\alpha = 0.10$ (1-sided)
Final	Z	1.6449	1.2816
N: 82	p (1-sided)	0.0500	0.1000
Events: 72 (approximately 108 events across 3 treatment groups)	~HR at bound	0.6786	0.7393
Month: 20.4	P (Cross) if HR = 1	0.0500	0.1000
	P (Cross) if HR = 0.6	0.7041	0.8147
Analysis	Value	$\alpha = 0.05$ (1-sided)	$\alpha = 0.10$ (1-sided)
Final	Z	1.6449	1.2816
N: 94	p (1-sided)	0.0500	0.1000
Events: 82 (approximately 123 events across 3 treatment groups)	~HR at bound	0.6954	0.7535
Month: 20.0	P (Cross) if HR = 1	0.0500	0.1000
	P (Cross) if HR = 0.6	0.7522	0.8509
Analysis	Value	$\alpha = 0.05$ (1-sided)	$\alpha = 0.10$ (1-sided)
Final	Z	1.6449	1.2816
N: 100	p (1-sided)	0.0500	0.1000
Events: 87 (approximately 130 events across 3 treatment groups)	~HR at bound	0.7028	0.7597
Month: 19.9	P (Cross) if HR = 1	0.0500	0.1000
	P (Cross) if HR = 0.6	0.7736	0.8665

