6.3. Measures to Minimize Bias: Randomization and Blinding

All participants will be centrally assigned to study treatment using an IRT. Full details will be provided in the IRT Manual.

Study treatment will be dispensed at the study visits summarized in the SoA (see [Table 3](#)).

Centralized randomization numbers within each stratum will be created for treatment assignment. Participants will be assigned to study treatment in accordance with the randomization schedule. Participants, investigators, the sponsor, and the study team will be blinded to treatment assignment. See emergency unblinding procedures in [Section 9.6](#).

A sponsor statistician who is not part of the study team will be unblinded and may provide summary aggregated data by treatment group to the DSMB, but individual participant data will remain blinded.

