10.1. Sample Size Determination

The sample size calculation is based on the primary endpoint of PFS. Approximately 162 participants will be randomized in a 1:1:1 ratio into TG1:TG2:TG3. The study is event-driven and will be complete after approximately 94 PFS events have been observed between TG1 and TG2 or between TG1 and TG3 (approximately 140 PFS events across the 3 treatment groups). Based on a target of 94 PFS events for all participants at the final analysis between TG1 and TG2 or between TG1 and TG3 (approximately 140 PFS events across the 3 treatment groups), which is expected to occur about 20 months from the start of enrollment, the study has approximately 80% power to detect an HR of 0.6 at an overall alpha level of 5% (1-sided) favoring one of the combination therapies with the assumption of study parameters as specified in Table 17 for PFS.

The sample size and power calculations were performed in R package "gsDesign."

Table 17: Sample Size Assumptions for Progression-Free Survival

Variable	Assumptions
Median PFS in TG1 (All participants)	3 months ^a
Randomization ratio	1:1:1
Assumed HR (All participants)	0.6
Enrollment duration	12 months
Follow-up for PFS	8 months
Assumed annual dropout rate	1%

^a Burtneess et al 2019.

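### The final-analysis triggers in SAP 3.2 are not equivalent and conflict with each other and with Protocol 10.1; the likely cost in power is small, but one blinded trigger should be named

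*SAP*

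**What the plan says.** SAP 3.2 sets the timing in one sentence with three parts. The first is a pairwise count: "The final analysis will be performed after approximately 94 PFS events have been observed between TG1 and TG2 or between TG1 and TG3". The second, in parentheses, is a pooled count of about 140 events over the three groups. The third is a time limit: "or the last participant has been followed up for at least 8 months after randomization, whichever is earlier". Further down, the same section describes the 8-month analysis as something that may be done if events are delayed, with follow-up time monitored across blinded groups.

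Protocol 10.1 has the two counts but no time limit: "The study is event-driven and will be complete after approximately 94 PFS events". SAP 10.2 records the timing change as part of SAP Amendment 1; SAP 2.1 still bases the SAP on Protocol Amendment 2.

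Protocol 6.3 says: "Participants, investigators, the sponsor, and the study team will be blinded to treatment assignment". It provides an unblinded sponsor statistician outside the study team, but describes that role only as supplying aggregate data to the DSMB.

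On power, SAP 3.2 says that at 94 events "the study has approximately 80% power to detect an HR of 0.6 at an alpha level of 5% (1-sided"), and Table 2 pairs the two counts as "Events: 94 (approximately 140 events across 3 treatment groups"). Table 3 gives lower-event scenarios, the smallest being "Events: 72 (approximately 108 events across 3 treatment groups"), with N of 82, 94 and 100 per pair. SAP 10.1 ties these scenarios to the 8-month analysis.

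**The concern.** The analysis date affects every efficacy result, so two teams reading the same documents should arrive at the same date. Here they might not. Neither document says whether the pairwise or the pooled count governs, who counts events by pair, or whether the 8-month limit binds.

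The *or* also works in an unhelpful direction. Events come faster in a weaker arm, so the pair containing the weaker combination reaches 94 first and the more promising comparison is analysed with fewer than 94 events. Taking the earlier of events and time makes 94 a ceiling rather than a target, whereas the 80% power figure needs 94 to be reached.

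**Working it through.** **Inputs.** From Protocol Table 17 and SAP 3.2: control median PFS 3 months, HR 0.6, 54 per arm (108 per pair), 12 months' enrolment, 1% annual dropout, 1-sided alpha 5%. Assumed here: uniform accrual and exponential PFS.

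**The plan's own figures.** Power at d events is Φ(√d/2 × |ln 0.6| − 1.645). For d = 94: 4.848 × 0.5108 − 1.645 = 0.831, so power is 79.7% (stated 80.0%). With 1.2816 for 10% alpha it is 88.4%, as stated ("When the 1-sided alpha level is 10%, the statistical power is 88.4"%). For 87, 82 and 72 events the formula gives 77.0%, 74.8% and 69.9%; Table 3 has 77.4%, 75.2% and 70.4%. The plan's power figures reproduce.

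**Expected events.** For an arm with hazard λ = HR × ln 2/3, dropout hazard η = −ln(0.99)/12 and k = λ + η, at month T ≥ 12:

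E(T) = (54/12) × (λ/k) × [12 − (e^(−k(T−12)) − e^(−kT))/k]

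At month 20:
- Control: 4.5 × 0.9964 × (12 − 0.633) = 51.0
- HR 0.6: 4.5 × 0.9940 × (12 − 1.909) = 45.1
- Pair: 96.1 events, power 80.5%. Pooled with both HRs 0.6: 51.0 + 2 × 45.1 = 141.2

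So the 8-month limit costs nothing if the planning assumptions hold.

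**The *or* trigger.** TG3 has HR 0.6 and TG2 varies. Each row solves for the month at which TG1+TG2 reaches 94, and then for the month at which the pooled count reaches 140.

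| TG2 HR | Month TG1+TG2 = 94 | Pooled then | TG1+TG3 then | Power | Month pooled = 140 | TG1+TG3 then | Power |
|---|---|---|---|---|---|---|---|
| 1.0 | 16.2 | 133 | 86.2 | 76.6% | 17.7 | 91.0 | 78.6% |
| 0.8 | 17.2 | 135 | 89.5 | 78.0% | 18.4 | 92.8 | 79.3% |
| 0.6 | 19.0 | 138 | 94.0 | 79.7% | 19.6 | 95.3 | 80.2% |

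When both HRs are 0.6 the expected counts tie, but in any one trial chance puts one pair ahead. Simulation (6,000 trials) gives a mean of 92.1 events per pair and about 78.5% power. For TG2 HR 1.0 it gives 76.4%. Against 80%, the loss is therefore about 1 to 4 points.

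**Why 94 and 140 differ.** 94 × 1.5 = 141, which assumes that the third arm supplies half of a pair's events, 47. At the first row's trigger date TG3 supplies 39.2, so the pooled count is 94 + 39.2 = 133.

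**Pooled count that secures 94.** TG1+TG3 reaches 94 at month 19.0, with 50.2 and 43.8 events. If TG2 is null the pooled count is then 2 × 50.2 + 43.8 = 144.

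**The 8-month limit with slower events.** Month 20, HR 0.6, control medians assumed:
- 4 months: 48.1 + 40.4 = 88.5 events, 77.6%
- 5 months: 45.1 + 36.3 = 81.4 events, 74.5%
- 6 months: 42.2 + 32.8 = 75.0 events, 71.5%

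**Table 3.** Events/N is 72/82 = 0.88, 82/94 = 0.87 and 87/100 = 0.87, close to Table 2's 94/108 = 0.87. The table has therefore reduced enrolment and kept the planned event rate. With 108 per pair and the planned hazards, 72 events occur at month 13.2, not the tabulated 20.4. Having only 72 at month 20 would need a control median near 6.5 months.

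**The case against.** The strongest reply is that little depends on this. The pooled 140 stands in the same sentence as the pairwise count and can be monitored blind. SAP 3.2 also frames its shortfall scenarios by pooled counts. The power statement is conditional on 94 events, Table 3 prints the reduced power, and SAP 10.2 logs the timing change. SAP 7.3.2 reports a nominal p-value, and SAP 10.2 says that Type I error served sample size and not decisions. All of this stands, and it limits the consequence. It does not say which trigger governs, and it does not reconcile SAP 3.2 with Protocol 10.1.

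A reader might go further in two directions that the documents do not support.

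- **The trigger breaks the blind.** If someone announced that TG1+TG2 had reached 94, subtraction from the pooled total would give TG3's count (133 − 94 = 39 against an average of 47 in the other two arms). No document describes such an announcement, and an unblinded statistician exists outside the team. If the team learned only that one of the pairs had reached 94, it would not know which combination was the remaining arm. What the text supports is that the counting role is unassigned.
- **The 8-month rule means 70% power.** That figure belongs to 72 events per pair, which at month 20 would need a control median of more than twice the planned 3 months.

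**Conclusion.** The defect is in the definition of the trigger. SAP 3.2 offers rules that fall on different dates, one of which the blinded team cannot apply, and the status of the 8-month limit is contradictory within the SAP and absent from Protocol 10.1.

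Read literally, the pairwise *or* costs the better comparison about 1 to 4 points of power. The 8-month limit costs nothing as planned and about 2 to 9 points if the control median is 4 to 6 months (80 − 77.6 to 80 − 71.5). Slower enrolment alone does not create a shortfall: with 18 months' accrual a pair has 99.1 events at the limit. Table 3's power values are sound because they depend on events; its N and Month rows describe a smaller trial.

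These sizes rest on uniform accrual, exponential PFS and the assumed medians. The point should be fixed but is not critical: it does not show that the trial is materially underpowered.

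**What to change.** 1. In SAP 3.2 and Protocol 10.1, make one pooled PFS event count, taken without treatment codes, the governing trigger and delete the pairwise *or*. A count of 140 gives the effective pair 91 to 95 events (79% to 80% power). If 94 events are wanted there even when the other arm is null, the count is about 144.
2. Say, in the same words in both documents, whether the 8-month rule is mandatory or a fallback. This matters more with a pooled count: in simulation with both HRs 0.6, the 8-month date came before 140 pooled events in about 35% of trials, against about 8% for the pairwise trigger.
3. State power as 80% at 94 events per pair, and 77%, 75% and 70% at 87, 82 and 72, citing Table 3.
4. Recompute the N and Month rows of Table 3 for 108 per pair with slower event accrual.

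Cost: wording in two documents and one recalculated table. Against the literal pairwise rule, a count of 140 delays the analysis by 0.6 to 1.5 months (19.6 − 19.0; 17.7 − 16.2). A count of 144 delays it by just under 3 months if one arm is null (19.0 − 16.2). The stated power becomes conditional on the events reached.

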3.3. Schedule of Assessments

Refer to Protocol Amendment 2 dated 19 DEC 2023 for a full description of all study procedures and assessment schedules for this study.

